6.1.2.1 RECOMMENDED BRIGATINIB DOSE REDUCTION LEVELS

Table 1: Recommended Brigatinib Dose Reduction Levels

Starting Dose	Dose Reduction Levels				
	First	Second	Third	Fourth	Fifth
90mg QD	60mg QD	Permanently discontinue	Not applicable	Not applicable	Not applicable
180mg QD	120mg QD	90mg QD	60mg QD	Permanently discontinue	Not applicable

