Grade 1	Withhold the dose until pneumonitis returns to grade 0 (baseline), then resume at 90 mg and do not escalate. If pneumonitis recurs, permanently discontinue treatment.*
Grade 2	Withhold the dose until pneumonitis returns to Grade 0, then resume at 60 mg and do not escalate.* If pneumonitis recurs, permanently discontinue treatment.*
Grade 3	Permanently discontinue treatment.*
Grade 4	Permanently discontinue treatment.*

*Or in select cases per investigator discretion and discussion with Lead PI, consider continued use/shallower dose escalation as per Camidge et al, JTO 2019

BRIGATINIB DOSE MODIFICATION RECOMMENDATIONS FOR TREATMENT-RELATED PNEUMONITIS OCCURRING AFTER DOSE ESCALATION TO 180 MG QD:

Toxicity Grade (CTCAE v4.03)	Recommended Action
Grade 1	Withhold the dose until pneumonitis returns to grade 0 (baseline), then resume at the same dose. If pneumonitis recurs, permanently discontinue treatment.*
Grade 2	Withhold the dose until pneumonitis returns to Grade 0. Resume at 120 mg QD.* If pneumonitis recurs, permanently discontinue treatment.*
Grade 3	Permanently discontinue treatment.*
Grade 4	Permanently discontinue treatment.*

*Or in select cases per investigator discretion and discussion with Lead PI, consider continued use/shallower dose escalation as per Camidge et al, JTO 2019

6.1.2.3 DOSE MODIFICATION RECOMMENDATION TABLE FOR TREATMENT-RELATED ADVERSE EVENTS (EXCLUDING PNEUMONITIS)

Table 2: Brigatinib Dose Modification Recommendations for Treatment-Related Adverse Events (excluding pneumonitis)

Adverse Reaction	Severity*	Dose Modification
Hypertension	Grade 3 hypertension (SBP greater than or equal to 160 mmHg or DBP greater than or equal to 100 mmHg, medical intervention indicated, more than one anti-hypertensive drug, or more intensive therapy than previously used indicated)	
Withhold brigatinib until hypertension has recovered to Grade 1 or less (SBP less than 140 mmHg and DBP less than 90 mmHg), then resume brigatinib at same dose.Recurrence: withhold brigatinib until recovery to Grade 1 or less, and resume at next lower dose (Table 1) or permanently discontinue treatment.

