	Grade 4 hypertension (life-threatening consequences, urgent intervention indicated)	
Withhold brigatinib until recovery to Grade 1 or less (SBP less than 140 mmHg and DBP less than 90 mmHg), and resume at next lower dose (Table 1) or permanently discontinue treatment.Recurrence of Grade 4 hypertension: permanently discontinue brigatinib.
Bradycardia (HR less than 60 bpm)	Symptomatic bradycardia	
Withhold brigatinib until recovery to asymptomatic bradycardia or to a resting heart rate of 60 bpm or above.If a concomitant medication known to cause bradycardia is identified and

Adverse Reaction	Severity*	Dose Modification
		
discontinued or dose-adjusted, resume brigatinib at same dose upon recovery to asymptomatic bradycardia or to resting heart rate of 60 bpm or above.
 
• If no concomitant medication known to cause bradycardia is identified, or if contributing concomitant medications are not discontinued or dose-adjusted, resume brigatinib at next lower dose (Table 1) upon recovery to asymptomatic bradycardia or to resting heart rate of 60 bpm or above.
	Bradycardia with life-threatening consequences, urgent intervention indicated	
• Permanently discontinue brigatinib if no contributing concomitant medication is identified.• If contributing concomitant medication is identified and discontinued or dose-adjusted, resume brigatinib at next lower dose (Table 1) upon recovery to asymptomatic bradycardia or to a resting heart rate of 60 bpm or above, with frequent monitoring as clinically indicated.• Recurrence: permanently discontinue brigatinib.
Visual Disturbance	Grade 2 or 3 visual disturbance	Withhold brigatinib until recovery to Grade 1 or baseline, then resume at the next lower dose (Table 1)

Adverse Reaction	Severity*	Dose Modification
	Grade 4 visual disturbance	Permanently discontinue brigatinib
Creatine Phosphokinase (CPK) Elevation	Grade 3 CPK elevation (greater than $5.0 \times$ ULN)	
Withhold brigatinib until recovery to Grade 1 or less (less than or equal to $2.5 \times$ ULN) or to baseline, then resume brigatinib at same dose.If Grade 3 elevation of CPK recurs, brigatinib should be withheld until recovery to Grade 1 or less (less than or equal to $2.5 \times$ ULN) or to baseline, then resume at the next lower dose level per Table 1.

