	Grade 4 CPK elevation (greater than $10.0 \times$ ULN)	
Withhold brigatinib until recovery to Grade 1 or less (less than or equal to $2.5 \times$ ULN) or to baseline, then resume brigatinib at next lower dose (Table 1).If Grade 4 elevation of CPK recurs, permanently discontinue brigatinib
Lipase/Amylase Elevation	Grade 3 lipase or amylase elevation (greater than $2.0 \times$ ULN)	
Withhold brigatinib until recovery to Grade 1 or less (less than or equal to $1.5 \times$ ULN) or to baseline, then resume brigatinib at same dose.If Grade 3 elevation of lipase and amylase reoccurs, brigatinib should be withheld until recovery to Grade 1 or less (less than or equal to $1.5 \times$ ULN) or to baseline, then resume at the next lower dose level per Table 1.

Adverse Reaction	Severity*	Dose Modification
	Grade 4 lipase or amylase elevation (greater than 5.0 × ULN)	
Withhold brigatinib until recovery to Grade 1 or less (less than or equal to 1.5 × ULN) or to baseline, then resume brigatinib at next lower dose (Table 1).If Grade 4 elevation of lipase/amylase recurs, permanently discontinue brigatinib
Hyperglycemia	Grade 3 (greater than 250 mg/mL or 13.9 mmol/L) or greater	If adequate hyperglycemic control cannot be achieved with optimal medical management, withhold brigatinib until adequate hyperglycemic control is achieved and consider reduction to the next lower dose (Table 1) or permanently discontinue brigatinib..
Other	Grade 3	
Withhold brigatinib until recovery to baseline, then resume at same dose.Recurrence: withhold brigatinib until recovery to baseline, then resume at next lower dose or discontinue brigatinib (Table 1).
	Grade 4	
First occurrence: either withhold brigatinib until recovery to baseline and resume at next lower dose (Table 1) or permanently discontinue.Permanently discontinue brigatinib for recurrence.

bpm = beats per minute; DBP = diastolic blood pressure; HR = heart rate; SBP = systolic blood pressure; ULN = upper limit of normal

Adverse Reaction	Severity*	Dose Modification

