
*Graded per National Cancer Institute Common Terminology Criteria for Adverse Events Version 4.03 (NCI CTCAE v4).
 
Asymptomatic lab abnormalities may be excluded pending discussion with the lead PI. Hypertension grading should be based on persistent blood pressure readings on optimal therapy, rather than specific drug use for the therapy
		

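### Table 2's Grade 3 lipase/amylase row starts on either enzyme, but its recurrence rule is worded as if both must rise again before the dose is reduced

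*Combined protocol and SAP*

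**What the plan says.** Section 6.1.2.3, Table 2, sets dose modifications for treatment-related adverse events other than pneumonitis. The severity cell of the first lipase/amylase row reads "Grade 3 lipase or amylase elevation", defined as more than 2.0 × ULN. Two bullets follow:

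- The first withholds drug until recovery to 1.5 × ULN or less, or to baseline, and then resumes at the same dose.
- The second covers recurrence: "If Grade 3 elevation of lipase and amylase reoccurs, brigatinib should be withheld until recovery to Grade 1 or less" (or to baseline), "then resume at the next lower dose level per Table 1".

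The Grade 4 row for the same enzymes has the severity cell "Grade 4 lipase or amylase elevation" and joins the two names with a slash in its recurrence bullet. A footnote to the table adds: "Asymptomatic lab abnormalities may be excluded pending discussion with the lead PI".

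**The concern.** The row is entered on one enzyme, but the step-down is conditioned on two. The two bullets lead to different restart doses, so the conjunction decides what a patient receives after a second event. Lipase and amylase are separate tests, both in the laboratory panel at every scheduled visit (section 1.3), so a rise in one alone can be seen. A site following the recurrence bullet to the letter would put a patient with a repeat Grade 3 rise in one enzyme back on the dose at which it recurred. Three sites take part, and they should all apply the same rule.

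**Working it through.** The plan states no figure to reproduce. The check compares the wording of the rows and then reads the consequence from Table 1.

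**Step 1. Grade 3 recurrence rules in Table 2**

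| Row | Trigger for the row | Condition for the recurrence rule | Same condition? |
|---|---|---|---|
| Hypertension | Grade 3 hypertension | Recurrence of that event | Yes |
| CPK | Grade 3 CPK rise | Recurrence of that event | Yes |
| Lipase/amylase | Grade 3 rise in lipase *or* amylase | Grade 3 rise in lipase *and* amylase | No |
| Other | Any other Grade 3 event | Recurrence of that event | Yes |

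Three of the four keep their own trigger. The closest parallel is the CPK bullet, "If Grade 3 elevation of CPK recurs, brigatinib should be withheld until recovery to Grade 1 or less", which has nearly the same sentence structure and carries its trigger over unchanged.

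**Step 2. Follow one case through the row.** A patient on 180 mg has a Grade 3 lipase rise, is withheld, recovers and resumes at 180 mg. Lipase then reaches Grade 3 again while amylase does not.

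- Reading *or*: the recurrence bullet applies. Withhold to recovery, then resume at 120 mg.
- Reading *and*: the recurrence bullet is not met. The event still satisfies the row's trigger, and the first bullet is not limited to a first occurrence. Withhold to recovery, then resume at 180 mg.

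The withholding and the recovery threshold are identical. Only the restart dose differs.

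**Step 3. Size of the difference.** Inputs are the dose levels in Table 1 (section 6.1.2.1). Gap = current dose − next lower level; relative gap = gap ÷ current dose.

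| Dose at recurrence | Restart, *and* reading | Restart, *or* reading | Gap | Relative gap |
|---|---|---|---|---|
| 180 mg | 180 mg | 120 mg | 180 − 120 = 60 mg | 60/180 = 33.3% |
| 120 mg | 120 mg | 90 mg | 120 − 90 = 30 mg | 30/120 = 25.0% |
| 90 mg | 90 mg | 60 mg | 90 − 60 = 30 mg | 30/90 = 33.3% |
| 60 mg | 60 mg | Permanent discontinuation | n/a | n/a |

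The last two lines apply to both the 180 mg and the 90 mg starting rows of Table 1.

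**Step 4. Look for a statement that settles it.** No other section says whether one enzyme is enough for a Grade 3 recurrence.

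**The case against.** The best reply is that nobody would misread this. The row heading names the two enzymes as one category, the severity cell governs both bullets and says *or*, the verb refers back to the event that opened the row, and the Grade 4 row treats the enzymes as interchangeable. The phrase can also be taken distributively, as a rise in either listed enzyme. On that view this is an ambiguity with an obvious answer. Most of this stands: the intent is very probably *or*, and that is why the correction should be uncontroversial. It does not make the row consistent.

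A second reply is that, even read literally, the row merely falls silent on a single-enzyme recurrence and does not direct a restart at the same dose. This does not stand. The event still meets the row's trigger, and the first bullet contains no restriction to a first episode.

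A third reply concerns exposure. Table 2 gives recommendations. The footnote lets asymptomatic laboratory findings be set aside after discussion with the lead PI. Dose modifications are discussed at regular meetings and reported to the DSMC (section 10.1.4), and intolerable toxicity ends study treatment in any case (section 7.2). All of this stands and limits the number of patients who could be affected. The footnote is optional, however, and does not cover symptomatic events; where the rule is used, its wording still sets the restart dose. It is also fair to say that the 25% to 33% gaps are simply the spacing of Table 1 and say nothing about how often the problem would arise.

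**Conclusion.** The point holds as a minor wording error in an operative dose-reduction rule. Followed exactly as written, the Grade 3 lipase/amylase row restarts a patient with a single-enzyme recurrence one dose level too high, assuming that either enzyme was meant to count. The excess is 30 to 60 mg daily, or continued treatment at 60 mg where the drug should have been stopped.

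To be affected, a patient needs a treatment-related Grade 3 recurrence in one enzyme only, not set aside under the footnote, at a site taking the literal reading. The documents give no frequency for this, and in a trial planned to enrol about 23 patients the number could be zero. The primary endpoint, the secondary analyses, the sample size and the error rate are unaffected. The mismatch itself is certain; whether it would ever change a patient's dose is not.

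**What to change.** In the Grade 3 lipase/amylase row of Table 2, change *and* to *or* in the recurrence bullet, so that a repeat Grade 3 rise in lipase or amylase leads to the next lower dose level. The Grade 4 row needs no change. The cost is a one-word table correction in the next amendment, with no new data, procedure or analysis.

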6.1.2.4 MANAGEMENT OF ADDITIONAL SELECTED TREATMENT-RELATED ADVERSE EVENTS

HYPERTENSION

Blood pressure should be monitored and recorded at each visit. Hypertension detected by at least 2 blood pressure measurements should be graded according to NCI CTCAE, v4.03, which defines hypertension as a disorder characterized by a pathological increase in blood pressure: a repeated elevation in the blood pressure exceeding 140 mmHg for systolic and over 90 mmHg for diastolic. For patients who either develop hypertension or experience worsening hypertension during treatment with study drug, at the discretion of the investigator, antihypertensive medication should be initiated or optimized to achieve target blood pressure before interruption or dose reduction of the study drug. If hypertension is persistent despite adequate antihypertensive therapy—including titration of antihypertensive medication or introduction of additional antihypertensive medications—or if grade 4 hypertension develops, dose interruption and reduction is recommended according to the tables above.

BRADYCARDIA

Heart rate should be monitored and recorded at each visit. Brigatinib should be avoided in combination with other agents known to cause bradycardia (e.g., beta-blockers, nondihydropyridine calcium channel blockers, clonidine and digoxin) to the extent possible. For symptomatic bradycardia, dose interruption and reduction is recommended according to the tables above.

PHOTOSENSITIVITY

Photosensitivity to sunlight has occurred in patients treated with brigatinib. Patients should be advised to avoid prolonged sun exposure and tanning beds while taking brigatinib, and for at least 5 days after discontinuation of treatment. When outdoors, patients should be advised to

wear a hat and protective clothing, and to use a broad-spectrum UVA/UVB sunscreen and lip balm (SPF at least 30) to help protect against potential sunburn. For severe photosensitivity reactions (\geq Grade 3), brigatinib should be withheld until recovery to baseline. The dose should be modified accordingly.

NAUSEA AND EMESIS

Nausea should be treated with standard-of-care anti-emetics. Prophylactic anti-emetics may be used.

DIARRHEA

For grade 1 diarrhea, symptomatic care such as loperamide (Imodium[®], McNEIL-PPC, Inc.) may be given, or no intervention may be undertaken, according to the investigator's clinical judgment. For grade 2 diarrhea, administer loperamide at 4 mg, then 2 mg every 2 to 4 hours until the patient is symptom-free for 12 hours. No dose modification is necessary unless the patient does not tolerate brigatinib or the symptom recurs. For grade ≥ 3 despite loperamide, treatment will be withheld until recovery to grade ≤ 1 . Secondary prophylaxis in patients who have experienced diarrhea with brigatinib treatment is allowed. Other medications and supportive care may be added according to the institution's standard of care.

6.2 PREPARATION/HANDLING/STORAGE/ACCOUNTABILITY

6.2.1 ACQUISITION AND ACCOUNTABILITY

Brigatinib tablets will be provided by, Takeda Pharmaceuticals.

The appropriate study personnel will maintain records of study drug receipt and dispensing.

Patients are to be instructed on proper storage, accountability, and administration of brigatinib.

6.2.2 FORMULATION, APPEARANCE, PACKAGING, AND LABELING

Brigatinib drug product is supplied as film-coated tablets containing 30 mg of brigatinib active pharmaceutical ingredient. Other ingredients are typical pharmaceutical excipients (lactose monohydrate, microcrystalline cellulose, sodium starch glycolate, colloidal silica, and magnesium stearate). The tablet coating is composed of typical pharmaceutical grade coating components (talc, polyethylene glycol, polyvinyl alcohol, and titanium dioxide). The drug product is

manufactured under current Good Manufacturing Practice in accordance with approved procedures. Brigatinib will be supplied in white high-density polyethylene bottles with induction sealed caps or blister packs. Bottle or blister pack labels will bear the appropriate label text as required by governing regulatory agencies. At a minimum, such text will include product name, product strength, number of tablets, and lot number.

6.2.3 PRODUCT STORAGE AND STABILITY

Brigatinib tablets should be stored in accordance with the storage instructions on the label. The recommended storage condition for brigatinib is under 30°C. Do not refrigerate or freeze.

6.2.4 PREPARATION

The study pharmacist or designee at the site will be responsible for handling and dispensing brigatinib and completing associated documentary paperwork. Supplies are shipped to the investigative site at appropriate intervals, depending on patient accrual. The site must use an appropriate dispensing log/accountability form provided by the sponsor or an acceptable substitute used by the site. Each time study medication is dispensed for a patient, the following information must be recorded: the patient's initials, the patient's study number, drug product strength (e.g., 30 mg), quantity dispensed with the corresponding lot number, date of dispensation, and the initials of the person dispensing the drug. These logs are to be maintained by the study pharmacist in the pharmacy throughout the duration of the study and will be periodically verified by a representative of the sponsor.

6.3 MEASURES TO MINIMIZE BIAS: RANDOMIZATION AND BLINDING

This is a prospective, unblinded single arm phase 2 trial.

6.4 STUDY INTERVENTION COMPLIANCE

At clinic visits, patients will be asked by an investigator or coordinator about drug compliance and responses will be documented in the patient's chart. Unused study drug will be returned to the Investigational Pharmacy upon completion of each treatment cycle.

6.5 PROHIBITED THERAPY

At enrollment, additional systemic therapies for the treatment of lung cancer may not be taken concomitantly with brigatinib (eg, TKIs, immunotherapy, chemotherapy), but there will not be a

required washout period for prior systemic therapies, with the exception of systemic treatment with strong cytochrome p-450 (cyp)3a inhibitors, strong cyp3a inducers, or moderate cyp3a inducers, which are not permitted within 14 days of study enrollment (refer to current brigatinib IB version for comprehensive list).

Patients may be switched to regimens containing these therapies by the treating physician if brigatinib is discontinued due to progressive disease or brigatinib intolerance by the patient. Disease progression and the associated changes in therapy will be recorded, the patient will be removed from study treatment, and they will continue to be followed for survival (for up to 24 months from Day 1).

Use of alternative or herbal therapy while on study treatment is only allowed if no known interactions with the study medication exist and must be documented and approved by the sponsor.

6.6 CONCOMITANT THERAPY

Corticosteroids for the treatment of cancer-related symptoms from brain metastases or extracranial disease are allowed. Prophylactic corticosteroids in the absence of symptoms are discouraged. Corticosteroid agent, dose, frequency, and duration recommendations are at the discretion of the treating physician.

Medications taken and considered by the treating physician to be related to the patient's cancer will be recorded in the eCRF from first dose of study drug through 30 days after the last dose.

Brigatinib should be avoided in combination with other agents known to cause bradycardia (e.g., beta-blockers, nondihydropyridine calcium channel blockers, clonidine and digoxin) to the extent possible.

Potential drug interactions:

In vitro studies with human liver microsomes indicate that cytochrome P450 (CYP) 2C8 and CYP3A4 are involved in the human metabolism of brigatinib. Medications and dietary (grapefruit-containing products) or herbal products (St John's Wort) that are strong inhibitors or inducers of CYPs, in particular, CYP2C8 or CYP3A4, should be avoided. Brigatinib is not a reversible inhibitor of CYPs 1A2, 2B6, 2C8, 2C9, 2C19, 2D6, and 3A4/5, with IC50 values of >70 μ M. Brigatinib is also

not a metabolism-dependent or a time-dependent inhibitor of the CYPs tested. Hence, drug-drug interactions (DDIs) due to inhibition of CYPs by brigatinib are unlikely.

The list of drugs that interact with CYP450 enzymes (notably, CYP2C8 and CYP3A4, 5, and 7) can be found online at <http://medicine.iupui.edu/clinpharm/ddis/table.aspx> [Accessed: October 6, 2019]. Drugs listed should be avoided if possible. Note: The website should be used as a guideline and is not necessarily comprehensive. It is the investigator's responsibility to ensure that any drugs under consideration have not been newly identified as CYP inhibitors.

For reference, FDA label information for brigatinib may also be found at: https://www.accessdata.fda.gov/drugsatfda_docs/label/2017/208772lbl.pdf

7 STUDY INTERVENTION DISCONTINUATION AND PARTICIPANT DISCONTINUATION/WITHDRAWAL

7.1 DISCONTINUATION OF STUDY INTERVENTION (STOPPING RULES)

The Sponsor-Investigator has the right to terminate this study at any time. Reasons for terminating the study may include, but are not limited to, the following:

- The incidence or severity of adverse events in this or other studies indicates a potential health hazard to patients.
- Patient enrollment is unsatisfactory.

7.2 PARTICIPANT DISCONTINUATION/WITHDRAWAL FROM STUDY

Participants are free to withdraw from participation in the study at any time upon request. In addition, the investigator has the right to withdraw a patient from the study at any time. Reasons for withdrawal from the study may include, but are not limited to, the following:

- Patient withdrawal of consent at any time
- Any medical condition that the Sponsor-Investigator determines may jeopardize the patient's safety if he or she continues in the study.
- Sponsor-Investigator determines it is in the best interest of the patient.
- Patient non-compliance with study procedures as determined by investigator
- Lost to follow-up (see section 7.3).

Patients must discontinue study treatment if they experience any of the following:

- Intolerable toxicity as determined by the investigator.
- Progression of disease requiring an alternate therapy, in the opinion of investigator

- Pregnancy.
- Patient withdrawal of consent or decision to discontinue participation.

At the time of withdrawal, all study procedures outlined for the End of Treatment visit should be completed. Every effort should be made to obtain information on patients who withdraw from the study. The primary reason for withdrawal from the study or study drug discontinuation should be documented on the appropriate eCRF.

